5.3 REPORTING OF ADRS AND OTHER SAFETY INFORMATION

All ADRs and other safety information as defined above have to be documented on the specific electronic forms of the electronic data capturing (EDC) system.

Serious ADRs have to be entered *immediately* (within 24 hours) into the eCRF and should be transferred electronically to Octapharma.

Non-serious ADRs and other safety information should be reported upon recognition but no later than 10 days.

Patients undergoing home treatment should be asked to inform their treating physician immediately of any ADR, or other relevant safety information. The treating physician will assess the causal relationship for ADR and report the event as described above.

Octapharma will handle all ADRs as post-marketing safety reports and will report the cases in compliance with applicable regulations for pharmacovigilance.

5.4 LABORATORY INVESTIGATIONS

The type and timing of blood sampling for laboratory evaluations are at the full discretion of the responsible physician. If such blood sampling takes place, only abnormal and clinically significant abnormal parameters should be documented in the eCRF.

6 STATISTICAL CONSIDERATIONS

Statistical analysis of all parameters will be descriptive. SAS software will be used for the statistical analysis. All data will be listed in their entirety and will be presented in summary tables.

In general, all study parameters will be described using the following standard statistical parameters: arithmetic means, standard deviation, median, minimum and maximum. Frequency tables (absolute and relative frequencies) will be produced for categorical parameters.

The demographic data, indications for use, baseline values, and number of doses will be summarised descriptively. Tolerability and efficacy assessments made by the treating physicians will be presented by frequency tables and corresponding figures.

7 DATA HANDLING AND RECORD KEEPING

7.1 ELECTRONIC CASE REPORT FORMS

An electronic case report form (eCRF) at the sites via a web-based secure and validated EDC system will be used for each patient enrolled. Investigators and study nurses are allowed to enter or change data in the eCRF as long as they are registered on a Delegation of Authority Log. Access to the eCRF is made only via a compatible web browser (Internet Explorer or Firefox). Internet is required. All safety relevant information will be transferred electronically to Octapharma's Corporate Drug Safety Unit.

Monitors and data management will have access to the data in the eCRF without the possibility to modify data. They are able to create queries. Investigators need to reply to given queries in the eCRF. Data will be checked for plausibility and completeness. Investigators must provide missing or non-plausible data in the eCRF.

At the end, the Principle Investigator will electronically sign the eCRF. The eCRF pages that have been locked will be printed and stored in the Investigator's archives for at least as long as required by regulatory constraints after completion or discontinuation of the trial, together with the original informed consent forms (if applicable) and the patient identification list. The Sponsor will archive the whole eCRF database.

7.2 INVESTIGATOR SITE FILE

The Investigator is responsible for maintaining all adequate records to enable the conduct of the project to be fully documented. This includes, among others, this protocol and any subsequent amendments, a sample of the eCRF, all correspondence pertaining to the conduct of the project, other written information, financial aspects of the project, signed agreement between involved parties, a copy of the notification to competent authorities, ethics committees or hospital administration, if applicable.

The Investigator is responsible for maintaining a confidential patient identification code list which provides the unique link between named source records and eCRF data. The Investigator must arrange for the retention of this confidential list for the maximum period of time required by local regulations.

No study document should be destroyed without prior written agreement between the Investigator and the Sponsor. Should the Investigator elect to assign the study documents to another party, or move them to another location, the Sponsor must be notified in writing.

7.3 DATA PROTECTION

In accordance with applicable regulations, all patient data documented on the eCRFs are to be pseudo-anonymised by the treating physician. Only the treating physician, or a person authorised by the treating physician, will be able to decode the patient identity using an internal patient allocation list.

Informed consent for the inclusion of a patient into this non-interventional study may or may not be required depending on the country; signing of a data privacy statement maybe sufficient for most countries. However, the treating physician is advised to always inform the participating patient about their inclusion in this NIS and the use of their pseudo-anonymised data in reports. This process should be documented in the patients' records.

If requested by national regulations governing the performance of non-interventional clinical studies, this NIS protocol (and any other documentation to be provided to patients, like patient diaries) has to be submitted to the Ethics Committee in charge for the hospital/institution where the NIS is conducted.

7.4 FINAL REPORT

At the end of the NIS, a final report will be compiled within 1 year.

**REVISION HISTORY**

Version/Date	Version name	Section	Changes implemented
1.0/14 Apr 2020	FINAL 1.0		N/A (Initial version of this SAP)

**LIST OF ABBREVIATIONS**

The following abbreviations will be used within this SAP.

Abbreviation or special term	Explanation
ADR	Adverse Drug Reaction
ATC	Anatomical Therapeutic Chemical
BMI	Body Mass Index
CIDP	Chronic Inflammatory Demyelinating Polyradiculoneuropathy
cm	Centimetre
CSR	Clinical Study Report
DM	Dermatomyositis
eCRF	Electronic Case Report Form
g	Gram
GBS	Guillain-Barré Syndrome
hr	Hours
ICH	International Conference on Harmonization
ICSR	Individual Case Safety Report
ITP	Immune Thrombocytopenic Purpura
IVIG	Intravenous Immunoglobulin
kg	Kilogram
MedDRA	Medical Dictionary for Regulatory Activities
MG	Myasthenia gravis
min	Minutes
mL	Millilitre
MMN	Multifocal Motor Neuropathy
MS	Multiple Sclerosis
NIS	Non-Interventional Study
PID	Primary Immunodeficiency
PM	Polymyositis
PT	Preferred Term
PV	Pemphigus Vulgaris
SAP	Statistical Analysis Plan

---

SCIG	Subcutaneous Immunoglobulin
SID	Secondary Immunodeficiency
SD	Standard Deviation
SOC	System Organ Class
TEN	Toxic Epidermal Necrolysis
TFLs	Tables, Figures and Listings

Property of Octapharma. Do not copy or distribute without written permission.

## **1 INTRODUCTION**

The purpose of this Statistical Analysis Plan (SAP) is to provide detailed descriptions of the statistical methods, data derivations and data displays for study protocol GAM10-06 Version 06 “Non-Interventional Study on the Tolerability of IVIG and SCIG” dated 27-Jun-2018 for the final analysis. The table of contents and templates for the tables, figures and listings (TFLs) will be produced in a separate document.

Any deviations from this SAP will be described and justified in the Clinical Study Report (CSR).

The preparation of this SAP has been based on International Conference on Harmonization (ICH) E9 guideline.

All data analyses and generation of TFLs will be performed using SAS 9.4® or higher.

Property of Octapharma. Do not copy or distribute without written permission.

---

**2 STUDY OBJECTIVES****2.1 Primary objective(s)**

The primary objective is to document the safety and tolerability of octagam®, panzyga® and cutaquinig® in any indication, age group or treatment regimen.

**2.2 Secondary objective(s)**

The secondary objective is to document their efficacy in patients receiving treatment.

**2.3 Exploratory objective(s)**

Not Applicable

**2.4 Safety objective(s)**

This is the primary objective in this observational study

Property of Octapharma. Do not copy or distribute without written permission.

## **3 STUDY DESIGN**

### **3.1 General study design**

This is a prospective, multicentre, non-interventional study (NIS).

The treating physician decides whether, how and for how long a patient is to be treated with octagam®, panzyga®, and/or cutaquinig®.

octagam®, panzyga®, and/or cutaquinig® will be prescribed regularly to any patient who needs to be treated with an IgG product because of their medical condition and whom the treating physician wants to include in this observational study, after the decision has been made to prescribe IVIG or SCIG treatment. This study will observe 300-500 patients treated with octagam®, panzyga® and/or cutaquinig® in any indication, age group, gender or treatment regimen. It is not possible to specify the exact number of doses per patient that are to be documented because of the different indications for use.

This observational study is conducted in outpatient and inpatient centres globally.

### **3.2 Randomization and blinding**

This is a non-randomized open-label observational study.

### **3.3 Study treatments and assessments**

Patients documented in this NIS will receive commercially available octagam®, panzyga® or cutaquinig® prescribed by a physician. Dosage and duration of treatment is at the sole discretion of the investigator and will depend on the type and/or severity of the disease and the patient's clinical condition.

Due to its non-interventional and observational nature, this study will strictly exclude predefined visits or time schedules (except that a close-out visit should take place before a patient leaves the NIS). However, it is recommended to perform subsequent visits on regular intervals according to standard treatment procedures for the respective disease. Table 1 lists all assessments recommended by the protocol.

**Table 1: Assessment Schedule**

Assessments	Baseline or Entry Visit	Subsequent Infusion Visits	Close-out Visit
Baseline Assessments	✓		
Previous IVIG and SCIG treatments	✓		
Concomitant medication(s)	✓	✓	✓
octagam®/panzyga®/cutaqui® treatment details		✓ 	
Information on efficacy		✓	✓
Adverse Drug Reactions (ADRs)		✓ 	✓
Checking of patient diary for patients doing cutaqui® home treatment		✓	✓

May take place at the same day as baseline/entry visit.

### 3.4 Primary endpoint(s)

The primary endpoint of this study is the incidence (count and frequency) of ADRs.

### 3.5 Secondary endpoint(s)

Secondary endpoint in this study is the efficacy of the IVIG/SCIG measured as:

For patients with diagnosis primary immunodeficiency (PID) or secondary immunodeficiency (SID):

- For each fourth infusion visit (starting with infusion visit 4) and the close-out visit: Influence of the treatment with IVIG/SCIG on the frequency, intensity and duration of infections and the consumption of antibiotics since the last visit.
- For each fourth infusion visit (starting with infusion visit 4) and the close-out visit: Occurrence of infectious episodes since the last visit.

For patients with other diagnoses than PID or SID:

- For each infusion visit and the close-out visit: Development of the clinical appearance of disease since the last visit.

---

- At the close-out visit: Influence of IVIG or SCIG treatment on the course of the disease.

**3.6 Exploratory endpoint(s)**

Not Applicable

**3.7 Safety endpoint(s)**

In this study, the safety endpoint is equal to the primary endpoint.

Property of Octapharma. Do not copy or distribute without written permission.

---

**4 SAMPLE SIZE AND POWER**

No formal sample size calculation was conducted for this study. This study will observe 300-500 patients.

Property of Octapharma. Do not copy or distribute without written permission.

## **5 ANALYSIS POPULATIONS**

No analysis populations have been defined in the study protocol. For the purpose of the statistical analysis the following two populations will be considered:

### **5.1 Enrolled population**

The Enrolled population will consist of all patients for whom baseline assessments are available, irrespective whether these patients were treated with any study drug.

The Enrolled population will be used in the summary of patient disposition.

### **5.2 Safety population (Safety)**

The Safety population will consist of all patients who had at least one infusion of any study drug.

The Safety population will be used for all analyses except the analysis of disposition. Patients will be included in the analysis according to the actual treatment received. As patients are allowed to change the study drug during the course of the study, treatment groups can be defined that are composed of more than one treatment depending on which patterns of treatment change will be actually observed.

### **5.3 Protocol deviations/violations and exclusions from analysis sets**

In this NIS, no protocol deviations/violations have been collected and no per-protocol population will be defined.

## 6 STATISTICAL CONSIDERATIONS AND ANALYSIS

### 6.1 Derived Variables

The below table provides the list of derived variables for demographic and baseline characteristics, various duration derivations and other important derivations applicable for this study.

Variables	Formula
Demographic and baseline characteristics	
Age at baseline (in years)	Year of the baseline visit – year of birth
Body mass index (BMI) (kg/m  )	Baseline weight (kg)/[height (m)]  . Round to two decimal places.
Derivation of durations	
Study day at any visit	Date of interest – date of first IVIG/SCIG infusion. One day is added if this difference is $\geq 0$
Treatment duration (in months)	(Date of last infusion with IVIG/SCIG – Date of first infusion with IVIG/SCIG + 1)/30.4375. Round to one decimal place.
Study duration (in months)	(Maximum(Date of close-out visit, date of last infusion with IVIG/SCIG) - Date of first infusion with IVIG/SCIG + 1)/30.4375. Round to one decimal place.
Derivation of exposure related measures	
Dose per infusion (g)	Infusion volume (mL) x strength where strength = 0.05 for octagam® 5% strength = 0.1 for octagam® 10% and panzyga® strength = 0.165 for cutaqui®
Dose per infusion (g/kg body weight)	Dose per infusion (g)/weight (kg), weight as measured at the respective infusion visit. Round to two decimal places.
Maximum infusion rate (mL /kg body weight/hr)	See section 7.4.2 for necessary transformations. Round to two decimal places.

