3.1.3 Flowchart of Study Events

Due to its non-interventional and observational nature, this study will strictly exclude pre-defined visits or time schedules (except that a close-out visit should take place before a patient leaves the NIS). However, it is recommended to perform subsequent visits on regular intervals according to standard treatment procedures for the respective disease.

Table 1 lists all assessments recommended by this protocol.

Table 1: Assessment schedule

Assessments	Baseline or Entry Visit	Subsequent Infusion Visits	Close-Out Visit
Baseline assessments	✓		
Previous IVIG and SCIG treatments	✓		
Concomitant medication(s)	✓	✓	✓

octagam®/panzyga® /cutaquig® treatment details		✓ ¹	
Information on efficacy		✓	✓
Adverse drug reactions (ADRs)		✓ ¹	✓
Checking of patient diary for patients doing cutaquinig® home treatment		✓	✓

¹ May take place at the same day as baseline/entry visit.

Data obtained during the study will be recorded, for this purpose Electronic case report forms (eCRF), namely a secure web-based data entry system (see Section 7.1), will be used.

The eCRF will consist of 4 main sections:

- 1) Baseline documentation: Must be completed when a new patient is enrolled. The patient's demographic data (year of birth or age, gender, weight, general condition, risk factors), medical history, basic disease (including date of diagnosis and details on previous treatments), and concomitant medications and diseases are to be documented.
- 2) Treatment record: Treatment details with octagam®/panzyga®/cutaquig® are to be documented, including date of administration, method of administration, infusion speed, dosage, batch number, concomitant medications incl. treatment details, if applicable. In case of home treatment with cutaquinig®, patients will be asked to fill in a study diary to carefully document information (ie. including date and method of administration, infusion speed, dosage, batch number; concomitant medications incl. treatment details, if applicable).
- 3) Suspected ADRs occurring during or after administration of octagam®/panzyga®/cutaquig® are to be recorded on separate ADR forms. Patients are to be advised to document in their diaries every ADR they experience at home, also in case they do not need any medical treatment.
- 4) Efficacy assessment: Available efficacy data are to be documented.

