3.1.4 Study Duration

This study started in August 2011 in 4 European countries and was then extended to Canada. The European centres are now closed or being closed and the study will continue in Canada. Planned study end is 2022.

The duration of observation for an individual patient will be as long as any of the described IVIGs or the SCIG will be prescribed by the treating physician and until the next regularly scheduled visit of the patient after last infusion. For patients with PID or SID the observation period should last at least 12 months, if possible.

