### 6.2 Handling of missing data and outliers

#### 6.2.1 Missing data analysis methods

For the handling of missing numbers of infections, see sections 7.3.2 and 7.5.2. Missing values of body weight in the calculation of measures of exposure will be handled as described in section 7.4.2. Otherwise, missing data will not be imputed for any analysis. For the handling of missing or incomplete start and end dates of Individual Case Safety Reports and medications, see section 6.2.2.

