## 7.3 Demographics and baseline characteristics

### 7.3.1 Demographics

Age (years), height (cm), weight (kg) and BMI (kg/m^2) at baseline will be summarized descriptively by treatment group and overall in the Safety population. The baseline weight will be defined as the weight measured before the first IVIG/SCIG infusion. Age category (categorized by age groups < 18, 18-43, 44-68, and > 68 years), race and sex will be summarized by counts and frequencies.

In addition, demographic characteristics will also be presented by diagnosis.

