### 7.6.1 Individual Case Safety Reports (ICSRs) and Adverse Drug Reactions (ADRs)

There will be a clear differentiation between ‘cases’ and the individual symptoms reported. This distinction is reflected in the eCRF by the possibility to enter several symptoms on a single ADR form. The following terminology is used in this document to clearly reflect this differentiation:

ADR = A single symptom or term reported; always coded to an individual MedDRA preferred term (PT).

Individual Case Safety Report (ICSR) = All reported symptoms or terms that are related to one and the same infusion (except re-challenges – to be counted also as one ICSR).

The assessment of severity and relatedness to study drug will be done on the case level.

For all analyses (except the listing of ICSRs leading to death), cases recorded on the ADR form of the eCRF but rated as “not related” will be excluded. Further, cases recorded on the ADR form but with a start date before the first IVIG/SCIG infusion will be excluded from all summaries as well but will be included in the listings if not rated as “not related”.

An overview table will show the count and percentage as well as the number of ICSRs regarding the occurrence of any ICSR, any serious ICSR, and any ICSR leading to withdrawal of study drug by treatment group and overall. Percentages will be calculated with two different denominators:

- Number of patients in the respective treatment group

- Number of infusions in the respective treatment group.

This overview table will also be presented by diagnosis.

The tabulation of count and percentage of ADRs and serious ADRs will be based on PTs and SOCs of the MedDRA thesaurus. MedDRA version 23.0 will be used for coding. Percentages again will be calculated based on the number of patients and on the number of infusions by treatment group and overall.

These summaries of ADRs will also be presented by diagnosis, by country (Austria, Spain, France, UK and Canada) and by age group (age categories < 18, 18-43, 44-68, and > 68 years).

All ICSRs will be listed, in addition, there will be separate listings for

- ICSRs leading to death (this listing will also include cases rated as “not related”).
- Serious ICSRs
- ICSRs leading to withdrawal of study drug.

In summaries by SOC and PT, ADRs will be sorted by decreasing frequency in the overall group by SOC and then by PT within SOC.

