**7.7 Other analyses****7.7.1 Subgroup analysis**

All summaries will also be generated by the underlying diagnosis. In addition, summaries of ICSRs and ADRs will also be generated by country (Austria, Spain, France, UK and Canada) and by age group (age categories < 18, 18-43, 44-68, and > 68 years).

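### Age as a difference of calendar years is either right or one year too high, so a few patients near 18, 44 and 69 are counted in the older group

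*SAP*

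**What the plan says.** SAP 6.1 gives one rule for age at baseline: "Year of the baseline visit – year of birth". It has no term for month or day and no branch for an age recorded by the site.

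Protocol 3.1.3 lists what the baseline form collects: "The patient's demographic data (year of birth or age, gender, weight, general condition, risk factors". So a site may enter a year of birth or an age. A full date of birth is not requested.

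Derived age feeds three places:
- SAP 7.3.1: "Age category (categorized by age groups < 18, 18-43, 44-68, and > 68 years), race and sex will be summarized by counts and frequencies".
- SAP 7.6.1, where ADR summaries are repeated "by age group (age categories < 18, 18-43, 44-68, and > 68 years", among other splits.
- SAP 7.7.1, where "summaries of ICSRs and ADRs will also be generated by country" and by the same four age groups.

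On missing values, SAP 6.2.1 lists its exceptions and then says: "Otherwise, missing data will not be imputed for any analysis".

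**The concern.** A calendar-year difference credits every patient with this year's birthday, whether or not it has happened. The errors therefore do not cancel: each one adds a year. Most patients stay in the same age group despite this. Those whose completed age is 17, 43 or 68 do not, because an added year moves them to the next group, and nobody moves the other way.

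The 18-year cut matters most. The plan tabulates ADRs separately for patients under 18. Some 17-year-olds would leave that group, and their reactions would appear in the 18-43 column. The paediatric group is probably one of the smaller ones, so even a few patients could show in its counts.

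**Working it through.** The plan states no figure on this point, so there is none to reproduce.

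**Inputs from the documents**
- Age rule: SAP 6.1.
- Cuts at 18, 44 and 69: SAP 7.3.1, 7.6.1 and 7.7.1.
- Cohort of 300-500: Protocol 3.1.1 and SAP 4.
- Calendar span, Protocol 3.1.4: "This study started in August 2011 in 4 European countries and was then extended to Canada"; "Planned study end is 2022".

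**Assumptions (not in the documents)**
- Birthdays and baseline visits are spread evenly over the year.
- For patient counts only, ages are uniform over 0-90.

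**Step 1: size and direction of the error.** Let t be the visit date and b the birthday, each as a fraction of the year. Derived age minus completed age is 1 if b > t and 0 otherwise, so it is never negative. For a given visit date, P(b > t) = 1 − t. Averaged over the year, ∫₀¹ (1 − t) dt = 0.50.

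A simulation of 1,000,000 patients per scenario agrees. With visits spread over August 2011 to December 2022, 48.8% were one year too old. With visits from August 2011 to the SAP's date in April 2020, 49.6% were. None was too young. In both scenarios 49.1% of patients with completed age 17 fell in 18-43.

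**Step 2: dependence on season.**
- All visits in the first quarter: mean t is 0.125, and 1 − 0.125 = 87.5% (simulated 87.5%).
- All visits in the fourth quarter: mean t is 0.875, and 1 − 0.875 = 12.5% (simulated 12.4%).

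**Step 3: share of minors who move.** If ages are uniform over the 18 single years 0-17, 0.5/18 = 2.8% of under-18s move to the adult group. Among those aged 13-17 the share is 0.5/5 = 10%.

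**Step 4: number of patients.**
- One cut: 0.5/90 = 0.56% of the cohort, or 1.7 of 300 and 2.8 of 500. That is about 2-3 patients.
- All three cuts: 3 × 0.5/90 = 1.67%, or 5.0 of 300 and 8.3 of 500. That is about 5-8 patients. The simulation gave about 1.6%.
- If 17-year-olds are instead 0.5% to 2% of the cohort, the number crossing the 18-year cut runs from 300 × 0.005 × 0.5 = 0.75 to 500 × 0.02 × 0.5 = 5.

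**Step 5: a 1 July birth date instead.** For visits from 1 July on, this gives the same age as the SAP rule. For visits before 1 July it gives one year less, and is wrong only if b ≤ t.
- Too high: ∫ from 0.5 to 1 of (1 − t) dt = 12.5%.
- Too low: ∫ from 0 to 0.5 of t dt = 12.5%.
- Total: 25%, against 50%.

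Before 1 July, t is smaller than 1 − t, so the expected error rate is never above that of the SAP rule on any visit date. The balance does depend on even spread. If all visits fell in the first quarter, 12.5% would be too low and none too high.

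**The case against.** **The data limit what can be done.** The baseline form asks for year of birth or age, and patient data are pseudo-anonymised (Protocol 7.3). No rule recovers exact completed age from a year of birth. This stands: some error of up to one year is unavoidable. It does not follow that an error in one direction is unavoidable.

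**The year difference is a fair estimate of decimal age.** With visits spread over the calendar, its mean error against exact age is between −0.01 and 0.00 years. This also stands, so the rule does little harm to the summary of mean age. The tables, however, cut at whole years, and a group labelled under 18 is ordinarily read in completed years.

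**The 1 July rule has its own defects.** An infant born in March and seen in May of the same year would get an age of −1, so the rule needs a floor at 0. It also moves some 18-year-olds into the paediatric group. Both are true, but the total error is still halved.

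**Three stronger readings are tempting but not supported.**
- A reader might infer that patients with only a recorded age drop out of every age table because SAP 6.2.1 bars imputation. Using a recorded age is not imputation. The eCRF is not shown, so whether any such patients exist is unknown. The SAP is merely silent on the case.
- A reader might infer that age group is an analysis dimension of the primary objective. The objective names age group to say that no one is excluded. The primary endpoint (SAP 3.4) is ADR incidence, and age group is one descriptive split of it.
- A reader might infer from the 50% figure that the safety results are materially distorted. Step 4 shows that only a few patients change group.

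**Conclusion.** The concern holds as a minor point. The SAP's age rule errs only upward against completed years, and at 18, 44 and 69 it moves patients only into the older group. The proportion of about half rests on evenly spread birthdays and visit dates. The documents give no enrolment calendar, but a study period from 2011 to 2022 makes that reasonable. The patient counts rest on an assumed age distribution and should be read as an order of magnitude. Overall ADR incidence does not change, and the safety and efficacy analyses involve no statistical tests. What is at stake is the accuracy of the age-group columns, above all the paediatric one.

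**What to change.** In SAP 6.1, replace the age rule with:
1. Use the age recorded at baseline where the eCRF holds one.
2. Otherwise, use completed years from 1 July of the birth year to the date of the baseline visit, with a minimum of 0.
3. Use this age for all age categories in SAP 7.3.1, 7.6.1 and 7.7.1.

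Add a footnote to the age-group tables saying that age may come from either source and that an error of up to one year remains at the cuts. State also whether the same age is used for the continuous summary and the listings. If it is, mean age falls by about half a year under even spread, because half of the visits (those before 1 July) lose one year.

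The cost is a few lines in the SAP and a small program change, with no new data collection. The drawback is that two sources of age are mixed in one variable.
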